3.1.2. Secondary

To assess the **safety and** efficacy and PK/PD of PZQ administered at different dose regimens.

- 3.1.2.1. To evaluate the PK/PD of both PZQ enantiomers given the concern that this has varied in studies of *S. mansoni*.
- 3.1.2.2. To expand PD endpoints for drug efficacy to include state-of-the art antigen tests to accurately capture residual worm burden (Circulating Cathodic and Anodic Antigens (CCA and CAA)).
- 3.1.2.3. To assess the safety and impact of PZQ treatment (dose and interval) on key measures of morbidity 6 and 12 months after initial treatment and mechanisms mediating morbidity
- 3.1.2.4. To further evaluate the safety of higher PZQ dosing (80 mg/kg) including bone marrow, renal, and liver toxicity as captured before dosing and 12 hours after.
- 3.1.2.5. To evaluate the impact of different doses (40 vs. 80 mg/kg) and varying dosing intervals (every 6 or 12 months) on iron status, hemoglobin, and age and gender adjusted longitudinal growth and nutritional status as captured by height and weight for age, and weight for height z-scores as determined by WHO Anthro.
- 3.1.2.6. To evaluate the mechanistic role of *Environmental Enteric Dysfunction (EED)* in the pathogenesis of schistosomiasis related morbidities. We will capture state of the art biomarkers of EE including fecal calprotectin, urine lactulose:mannitol ratio, serum

endotoxin, serum endotoxin core antibody, and pro- inflammatory cytokines and employ Path Modeling techniques to identify mechanistic pathways.

- 3.1.2.7. To assess the role of Environmental Enteric Dysfunction (EED) in inter-individual variability in PZQ area under the curve (AUC) PK parameters demonstrated in this age group.
- 3.1.2.8. To explore immune responses to *S. mansoni* infection and treatment
- 3.1.2.9. To assess the prevalence and the pattern of schistosomiasis-related morbidity as determined by ultrasound scan.

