4. STUDY DESIGN

4.1 Trial design

Four arm randomized double blind placebo-controlled trial with a 4 week, 6 months and 12 month follow up (Figure I). Half of the cohort will receive an additional PZQ dose (at the same dose given at baseline) at 6 months and half placebo. Parasitological endpoints will be measured at 4 weeks and at 6 months urine stored for future antigen testing. Morbidity endpoints will be assessed at 6 and 12 months.

Figure I Schematic of Study Design

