3. *Study Visit 3 (6 months post enrolment)* Six months (+/- 2 weeks) following visit one, subjects will return to the respective field laboratories. They will receive either the same dose of Praziquantel as received at Visit 1 or placebo as determined at baseline randomization. At this

visit, and before the study drug or placebo is received, blood will be drawn for follow up assessment of morbidity, and in depth measures of nutritional status. An ultrasound scan will be performed. Blood (7 ml) will be collected for the same subset of N=150 subjects for studies of immunological responses. Urine will be stored at this visit for future processing of CAA to monitor re-infection.

4. Study Visit 4, Close out. (12 months post enrollment) Twelve months (+/- 2 weeks) post enrollment and initial treatment, study subjects will return to the field laboratory. Prior to this visit they will be asked to provide three stool samples and one urine. At this visit, blood will be drawn for follow up morbidity studies and in-depth measures of nutritional status will be made. All children will be treated with Praziquantel and those infected with soil-transmitted helminths will be treated with albendazole 200 mg (12 – 24 month old children) or albendazole 400 mg (children over age two). A repeat ultrasound scan will be done before the participant is discharged from the study. If however, the ultrasound scan at six months revealed resolution of any pathology detected at baseline, there will be no repeat at discharge. Blood (7 ml) will be collected for the same subset of N=150 subjects for studies of immunological responses.

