7.5. Follow up at 6 months

The following activities will take place at the respective research laboratory. This visit will take approximately three hours with no overnight admission. Technical work in this phase will be performed by Ministry of Health personnel (Vector Control Division).

- **Admission** weight, height, clinical history
- **Stool** collection for:
 - Calprotectin and fecal occult blood (performed on site).
- **Urine** collection and storage for future processing of CAA. This will allow for monitoring of re-infection in the cohort.
- **PZQ or Placebo** administration at the study assigned dose after a meal consisting of local foods and monitoring for AE post-treatment

- **Blood:** Five ml for morbidity studies including CBC, iron biomarkers, EED biomarkers, pro-inflammatory cytokines and further 7 ml from the sub-group of N=150 children who were selected at baseline for immunology assays (such as flow cytometry, Luminex, ELISpot and ELISA). Before discharge, another blood sample will be removed between 6 – hours after administration of the first dose of the study drug. This enables monitoring for possible toxicity.
- **Ultrasound** to determine possible changes in baseline morbidity patterns

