7.6. Follow-up and close out at 12 months

The following activities will take place at the respective research laboratories. This visit will take approximately 5-6 hours with no overnight admission. Technical work in this phase will be performed by Ministry of Health personnel (Vector Control Division).

- Weight, height, clinical history
- Lactulose/Mannitol beverage. They will take 2ml/kg of lactulose-mannitol solution (containing 250 mg/mL lactulose and 50 mg/mL mannitol in purified water, in aliquots of 20ml) up to a maximum of 20 ml. Urine will be collected for 2 hours after ingestion of the solution. 2ml aliquots of each of the urine samples will be collected and stored between 2 – 8°C for lactulose-mannitol assay.
- **Urine** test for CAA/CCA assay
- **Stool** collection for:
 - Calprotectin and fecal occult blood (performed on site).
 - Kato Katz (two samples in Uganda and three in Philippines) with some collected prior to visit
- **Urine** collection for CCA and CAA
- **Blood:** Five ml for morbidity studies including CBC, iron biomarkers, EED biomarkers, pro-inflammatory cytokines and further 7 ml from the sub-group of N=150 children who were selected at baseline for immunology assays (such as flow cytometry, Luminex, ELISpot and ELISA).
- **PZQ** administration at the study assigned dose after a meal consisting of local foods for children infected with schistosomiasis based on Kato-Katz or urine CCA
- **Albendazole** administration for any child infected with soil-transmitted helminths

- **Ultrasound** to determine persistence of morbidity

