12. Mean haemoglobin level at 12 months
13. Proportion with anaemia at 12 months
14. Exploratory: EED markers
15. Exploratory: immune responses to *S. mansoni* infection and treatment
16. Exploratory: prevalence and pattern of schistosomiasis-related morbidity by ultrasound scan.

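### Omitting the 12-month ultrasound after resolution at 6 months makes recurrence unobservable in those children, and section 7.6 lists the scan without that exemption

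*Combined protocol and SAP*

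**What the plan says.** Section 4.2.1, Study Visit 4, first gives a general rule: "A repeat ultrasound scan will be done before the participant is discharged from the study". It then makes an exception: "If however, the ultrasound scan at six months revealed resolution of any pathology detected at baseline, there will be no repeat at discharge".

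Section 7.6 lists ultrasound among the 12-month activities, its purpose being "to determine persistence of morbidity", and sets no condition on the 6-month result. Other items in that list do carry limits. Praziquantel is "for children infected with schistosomiasis based on Kato-Katz or urine CCA", albendazole is restricted to children with soil-transmitted helminths, and the extra blood is restricted to the immunology sub-group. Section 7.5 lists the 6-month scan without condition, "to determine possible changes in baseline morbidity patterns".

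On timing, section 4.1 says "Morbidity endpoints will be assessed at 6 and 12 months". Section 3.1.2 includes the objective "To assess the prevalence and the pattern of schistosomiasis-related morbidity as determined by ultrasound scan", and 3.2.2.8 makes it a secondary outcome measure. Section 11.1 labels it exploratory (item 16: "prevalence and pattern of schistosomiasis-related morbidity by ultrasound scan") and gives no time point, hypothesis or test. Section 11.4 plans complete-case analysis without imputation and has no rule for scans omitted by design.

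**The concern.** Whether a child is scanned at 12 months depends on that child's own earlier result on the same outcome, measured after randomisation. This is missingness created by the design, and it falls on the children who responded.

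The trial asks whether six-monthly treatment does better than annual treatment. Arms 1 and 2 are treated identically up to the 6-month visit, and so are Arms 3 and 4. On ultrasound, any benefit of the 6-month dose must show between months 6 and 12, either as continued clearing in unresolved children or as less recurrence in resolved ones. The exception removes the second of these from view. An analysis rule written later cannot recover it, because no resolved child would have a 12-month scan.

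The conflict also matters for conduct. Staff following 7.6 and staff following 4.2.1 would scan different children, possibly differently at the two sites.

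**Working it through.** The documents give no ultrasound prevalence, resolution or recurrence rate and no power figure for this outcome, so there is no plan figure to reproduce. All rates below are assumptions. The only document figure used is the 540 children expected at 12 months (section 11.2), about 270 per interval group.

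**Notation.** b = share with pathology at baseline; r = share of those resolved at 6 months; q = share of resolved children with recurrence by 12 months; s = share of unresolved children still affected at 12 months.

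Among children with baseline pathology, 12-month prevalence is:
- if all are scanned: r·q + (1 − r)·s
- complete case under the 4.2.1 rule: s, since only unresolved children are scanned
- carrying resolution forward: (1 − r)·s, since every recurrence is counted as clear

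Neither of the last two contains q.

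**Interval comparison.** Assume s = 60% in both groups, and q = 10% with re-treatment and 30% with placebo. Because treatment is the same up to the 6-month visit, r is the same in both groups.

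| r | All scanned, re-treated | All scanned, placebo | True difference | Complete case | Carried forward |
|---|---|---|---|---|---|
| 30% | 0.03 + 0.42 = 45% | 0.09 + 0.42 = 51% | 6 points | 60% v 60% | 42% v 42% |
| 50% | 0.05 + 0.30 = 35% | 0.15 + 0.30 = 45% | 10 points | 60% v 60% | 30% v 30% |
| 70% | 0.07 + 0.18 = 25% | 0.21 + 0.18 = 39% | 14 points | 60% v 60% | 18% v 18% |

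The observed difference is exactly zero because s is set equal in the two groups. If re-treatment also lowered s, that part would be seen and the recurrence part still would not.

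**Whole group.** Suppose children clear at baseline are scanned and stay clear. Complete-case prevalence is then b(1 − r)s / (1 − b·r).
- At b = 20%, r = 50%: 0.06 / 0.90 = 6.7% in both groups, against a true 7.0% (re-treated) and 9.0% (placebo).
- At b = 40%, r = 30%: 0.168 / 0.88 = 19.1% in both groups, against a true 18.0% and 20.4%.

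The bias in the level can go either way. The loss of the recurrence difference does not depend on that.

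**Dose comparison.** Here r may differ by the 6-month scan. Assume r = 40% and 60%, q = 20% and s = 60% in both dose groups.
- All scanned: 0.08 + 0.36 = 44% and 0.12 + 0.24 = 36%, a difference of 8 points.
- Complete case: 60% and 60%, a difference of 0.
- Carried forward: 36% and 24%, a difference of 12 points.

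**Number of scans.** Children exempted = b·r·270 per interval group. At b = 20%, r = 30% this is 16; at b = 40%, r = 70% it is 76. Over 540 children the range is about 32 to 151.

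**The case against.** The case on the other side is substantial.

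- **The 7.6 conflict can be narrowed.** A reader might infer that 7.6 orders the scan for every child in so many words. It does not; it lists the scan without condition. Its stated purpose concerns persistence, and resolved pathology is not persisting, so the specific exception could be read into it. Against this, the same list spells out limits for three other items and none for ultrasound. The conflict is one of omission, but staff still need one instruction.
- **The estimand is not defined.** Section 11.1 confines the interval and dose hypotheses to outcomes 6 to 13. Baseline and 6-month scans, both unconditional, already give a prevalence and a pattern. This stands and limits the weight of the point. It does not make recurrence measurable, and 4.1 places morbidity endpoints at 12 months as well as 6.
- **The numbers may be small.** With 20% baseline pathology and half resolving, 0.20 × 0.5 × 270 = 27 children per interval group are exempt. Recurrence of 20% and 5% gives 5.4 and 1.35 children. If unresolved pathology persists, full scanning would compare 12.0% with 10.5%, with about 9% power. This stands as a limit on what a between-arm test could show. Resolution and recurrence can still be described by arm.
- **Counting rules can be set later.** Section 11.4 defers detail to a formal SAP, and its complete-case rationale refers to low loss at 4 weeks, so applying it to this outcome is an inference. A later rule can define how resolved children are counted; it cannot supply the missing scans.
- **The order of scan and dose at 6 months is not stated.** A reader might take it as given that the scan comes first. Section 4.2.1 places blood and nutritional measures before dosing but does not place the scan. The argument needs only that a same-day dose would not already show on ultrasound, which is an assumption.

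**Conclusion.** The point holds for ultrasound data only. Sections 4.2.1 and 7.6 differ on which children are scanned at 12 months. Following 4.2.1 leaves recurrence after 6-month resolution unobserved during the only period in which the interval groups are treated differently.

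Three stronger readings are not supported:
- That 12-month morbidity data in general are lost. Anthropometry, haemoglobin and the other 12-month measures do not fall under the exception.
- That more children are skipped in the better-treated interval group. The skip is decided at the 6-month visit, before the interval groups have diverged, so expected skip rates are equal. Unequal skipping is a concern for 40 against 80 mg/kg only.
- That the trial's main conclusion is at risk. The primary analysis is unaffected, and this outcome is exploratory with no specified test.

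The illustrated loss of 6 to 14 points among children with baseline pathology rests wholly on assumed rates, including equal persistence in unresolved children. The mechanism does not depend on those values, only on some resolved children recurring. The change is worth making because it is cheap and cannot be made up at analysis.

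**What to change.** Delete the exception in section 4.2.1 so that the 12-month scan is done as 7.6 lists it. Say in both sections that children clear at baseline are scanned too; the general rule implies this but does not state it. Report resolution at 6 months and recurrence at 12 months by arm.

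The cost is one deleted sentence and, on the assumed rates, roughly 32 to 151 non-invasive scans across both sites beyond what 4.2.1 requires. None is beyond what 7.6 lists. These children attend the 12-month visit anyway, and no new staff or type of procedure is needed.

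If the exemption is kept, add it to 7.6. State that recurrence after 6-month resolution is not assessed and that 12-month ultrasound prevalence will not be compared between arms.

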5. STUDY ENROLLMENT AND WITHDRAWAL

5.1. Subject Inclusion Criteria

- *S. mansoni* (Uganda) or *S. japonicum* (Philippines) infection of any intensity as determined by Kato-Katz
- Otherwise healthy as determined by history and physical examination conducted by the study physician at the second stage screening
- Age 12-47 months inclusive
- Parental consent to participate.

5.2. Subject Exclusion Criteria

- Parental inability to provide informed consent
- Significant disease/illness as determined by history or physical exam. This includes a severe acute illness or chronic disease as defined by greater than 3-months duration and significantly impacting a child's daily activities.
- Grade 3 or higher laboratory abnormality of BUN, Creatinine, bilirubin, white blood cell count, or platelet count will warrant exclusion. Grade 2 or higher abnormality of ALT or AST will warrant exclusion. Children with severe anemia as defined by hemoglobin less than 7.0 g/dl will be excluded.
- Severe wasting as defined by WHZ < -3SD
- Exposure to immuno-modulatory therapeutics such as steroids e.g. dexamethasone, prednisone and other medications such as chloroquine.
- Confirmed diagnosis of ocular cysticercosis.

5.3. Treatment Assignment Procedures

5.3.1. Randomization Procedures

Prior to study inception, the study biostatistician ([name]) will use a random number generator with randomly permuted block sizes, to assign study numbers to each of the four study arms. We will work with the pharmacist at International AIDS Vaccine Initiative (IAVI) who will pre-fill two vials per child for each study visit's two doses and the assigned study number. As a child is enrolled, they will be assigned the next study number. The arm to which they are randomized will determine both baseline dose and repeat dose versus placebo at the six-month visit.

5.3.2. Masking Procedures

At baseline, all subjects will be treated with 40 mg/kg followed by placebo or 80 mg/kg (40 mg/kg followed by 40 mg/kg). Study subjects and parents will not be informed of the dose received in the form of crushed tablets. Placebo will consist of tablets matched for size, shape, and color with the excipients from the active drug.

At the six month visit, subjects will receive either the same baseline dose or placebo, according to the group to which they were randomized at baseline.

5.3.3. Reasons for Withdrawal and Discontinuation of Study Product Administration

Subjects may voluntarily withdraw their consent for study participation at any time without penalty or loss of benefits to which they are otherwise entitled.

An investigator may also withdraw a subject from receiving the study product for any reason. Follow-up safety evaluations will be conducted, if the subject agrees. If a subject withdraws or is withdrawn prior to completion of the study, the reason for this decision must be recorded in the case report forms (CRFs).

The reasons, might include, but are not limited to the following:

- Subject no longer meets eligibility criteria
- Subject becomes noncompliant
- Medical disease or condition, or new clinical finding(s) for which continued participation, in the opinion of the investigator might compromise the safety of the subject, interfere with

the subject's successful completion of this study, or interfere with the evaluation of responses

- Subject lost to follow-up
- Determined by a physician's discretion to require additional therapy not indicated in the protocol to ensure subject's health and well-being (or treatment failure, if applicable)
- Voluntary withdrawal

If the subject consents, every attempt will be made to follow all AEs through resolution. The procedures that collect safety data for the purposes of research are included in the informed consent.

Investigators will inform the subject that already collected data will be retained and analyzed even if the subject withdraws from this study, unless they withdraw consent.

5.3.4. Handling of Withdrawals and Discontinuation of Administration

If subjects are withdrawn by study investigators due to newly diagnosed medical condition, they will be referred for treatment at the respective district hospitals. Subjects who voluntarily withdraw consent will be offered follow up screening for schistosomiasis and soil transmitted helminths and treatment provided as needed. No other nutritional or morbidity studies will be conducted as these are research only. In the unlikely event that a subject needs to discontinue product administration at later time points due to an AE or SAE, he/she will be asked to continue scheduled evaluations, complete an end-of-study evaluation, and be given appropriate care for symptoms of any AE until resolved or the subject's condition becomes stable.

5.3.5. Subject Replacement

Subjects withdrawn will not be replaced. Our sample size calculations allowed for withdrawal and expected rates of loss to follow up.

5.3.6. Termination of Study

If the study is prematurely terminated by the sponsor, any regulatory authority, or the investigator for any reason, the investigator will promptly inform the study subjects and assure appropriate therapy or follow-up for the subjects, as necessary. The investigator will provide a detailed written explanation of the termination to the IRB/IEC.

6. STUDY INTERVENTION/INVESTIGATIONAL PRODUCT

6.1. Study Product Description

[figure not shown]
6.1.1. Acquisition of Praziquantel

Praziquantel will be purchased from Macleods Pharmaceuticals, [name]. The study drug will be shipped by Thermo Fisher Scientific to the Tedor Pharmaceuticals in Rhode Island for compounding into vials. These will then be shipped by Thermo Fisher Scientific to the two study sites.

The study drug will be shipped at regular intervals to ensure doses do not expire.

6.1.2. Formulation, Packaging, and Labeling

Praziquantel is a trematodicide provided in tablet form for the oral treatment of schistosome infections and infections due to liver fluke. is 2-(cyclohexylcarbonyl)-1,2,3,6,7, 11b-hexahydro-4H-pyrazino [2, 1-a] isoquinolin-4-one with the molecular formula; C₁₉H₂₄N₂O₂. The structural formula is as follows:

Praziquantel is a white to nearly white crystalline powder of bitter taste. The compound is stable under normal conditions and melts at 136-140°C with decomposition. The active substance is hygroscopic. Praziquantel is easily soluble in chloroform and dimethylsulfoxide, soluble in ethanol and very slightly soluble in water.

Praziquantel tablets contain 600 mg of praziquantel. Inactive ingredients are corn starch, magnesium stearate, microcrystalline cellulose, povidone, sodium lauryl sulfate, polyethylene glycol, titanium dioxide and hypromellose.

6.1.3. Product Storage and Stability

Praziquantel is stable when stored below 86 °F (30° C). It will be stored at room temperature at the field laboratory with rigorous temperature monitoring. The field sites at Lake Albert, Uganda and Leyte, The Philippines have generators in case of electrical outage.

6.2. Dosage, Preparation and Administration of Study Intervention/Investigational Product

Praziquantel dosing will be calculated by study participant's weight as follows:

Arm 1: 40 mg/kg dose at baseline & Placebo 3 hours later//Placebo & Placebo 3 hours later at six months post baseline (N = 150)

Arm 2: 40 mg/kg dose at baseline & Placebo 3 hours later //40 mg/kg dose & Placebo 3 hours later at six months post baseline (N = 150)

Arm 3: 80 mg/kg dose at baseline split as 40 mg/kg and 40 mg/kg 3 hours later// Placebo & Placebo 3 hours later at six months post baseline (N = 150)

Arm 4: 80 mg/kg dose at baseline split as 40 mg/kg and 40 mg/kg 3 hours later//80 mg/kg dose split as 40 mg/kg and 40 mg/kg 3 hours later at six months post baseline (N = 150)

The pharmacy will provide single use vials with study numbers based on randomization group with sufficient study drug for the highest expected weight (4 year old at 80 mg/kg dose). Subjects will receive praziquantel at either 40 or 80 mg/kg at baseline based on the arm to which they are randomized. At six months, subjects will receive either 40 mg/kg or 80 mg/kg or placebo based on study arm.

Participant specific dose will be calculated and the adequate amount of 600mg tablets will be crushed for both praziquantel and placebo. The powder will then be mixed with a small amount of fruit juice for optimal suspension and delivery to the study participant. The dose will be given with a meal to improve absorption.

